11.3 Calculation or derivation of pharmacodynamic variable(s)

Analysis of the PD of clopidogrel will be the responsibility of the study biostatistician at Quintiles, Phase I services, Overland Park, USA. Quintiles SOPs and Work Instructions will be used as the default methodology if not otherwise specified.

If data permits, the following PD variables will be calculated:

mIPA Maximum inhibition of platelet aggregation calculated as

 $[1 - (postdose mPA) \text{ on Days } 2/6/15/30)/(mPA \text{ at baseline})] \times 100$

 Δ PRI Change in PRI calculated as [PRI (on Days 2/6/15/30) – PRI (at baseline) / PRI (on Day 1, predose)] × 100.

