The primary endpoint of this study is maximum inhibition of platelet aggregation (mIPA) based on maximum platelet aggregation (mPA) to 20 μ M ADP assessed at baseline and on Days 2, 6, 15, and 30. In addition, VASP (flowcytometric VASP-assay) parameters of platelet reactivity index (PRI) and change in platelet reactivity index (Δ PRI), exploratory PD endpoints, will be assessed at these same time points.

• Pharmacokinetics:

AUC, AUC_{0-t}, and C_{max} will be calculated after the loading dose of clopidogrel on Day 1 and AUC_{0-t,ss} and $C_{ss,max}$ on Days 5, 14, and 29 for clopidogrel active metabolite.

• Safety:

Adverse events, vital signs, and safety laboratory variables will be assessed throughout the study.

Statistical methods

Plasma concentrations of clopidogrel active metabolite and the derived PK parameters will be summarized by treatment using descriptive statistics.

Both PD and PK variables will be analyzed using a linear mixed effect analysis of variance (ANOVA) model with fixed effect for period, sequence, site, and treatment and a random effect for volunteer within sequence. The clopidogrel alone treatment will be the reference for the 3 test interaction treatment arms.

Safety data will be presented with descriptive statistics. Adverse events will be summarized by incidence within treatment. Laboratory safety tests and vital signs will be summarized by treatment group and time points within treatment groups.

TABLE OF CONTENTS

PAGE

	TITLE PAGE	1
	PROTOCOL SYNOPSIS	2
	TABLE OF CONTENTS	5
	LIST OF ABBREVIATIONS AND DEFINITION OF TERMS	9
1.	INTRODUCTION	12
1.1	Background	12
1.2	Research hypothesis	12
1.3	Rationale for conducting this study	12
1.4	Benefit/risk and ethical assessment	14
2.	STUDY OBJECTIVES	14
2.1	Primary objective	14
2.2	Secondary objectives	14
2.3	Exploratory objectives	15
3.	STUDY PLAN AND PROCEDURES	15
3.1	Overall study design and flow chart	15
3.2	Rationale for study design, doses and control groups	20
4.	VOLUNTEER SELECTION CRITERIA	20
4.1	Inclusion criteria	20
4.2	Exclusion criteria	21
5.	STUDY CONDUCT	23
5.1	Restrictions during the study	23
5.2	Volunteer enrollment and randomization, and initiation of investigational	
5.2.1	product	25
5.2.1		20
3.3	Procedures for handling volunteers incorrectly enrolled, randomized or initiated on investigational product	27
5.4	Blinding and procedures for unblinding the study	27
5.5	Treatments	
5.5.1	Identity of investigational product(s)	
5.5.2	Doses and treatment regimens	28

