Table 2	Laboratory variables					
Table 3	Volume of blood to be drawn from each volunteer					
LIST O	F FIGURES					
Figure 1	Study design17					
Figure 2	Treatment sequences					
LIST O	F APPENDICES					
Appendix	A Signatures					
Appendix	B Additional Safety Information					
Appendix	C International Airline Transportation Association (IATA) 6.2 Guidance Document					

LIST OF ABBREVIATIONS AND DEFINITION OF TERMS

The following abbreviations and special terms are used in this study Clinical Study Protocol.

Abbreviation or special term	Explanation
ADP	Adenosine diphosphate
AE	Adverse event
ALT	Alanine aminotransferase
AMC	active thiol metabolite of clopidogrel
ANOVA	Analysis of variance
AST	Aspartate aminotransferase
AUC	Area under the curve from time zero to infinity
$\mathrm{AUC}_{0\text{-t}}$	Area under the curve from time zero to last quantifiable concentration
AV	Atrioventricular block
BMI	Body mass index
BP	Blood pressure
CI	Confidence interval
C_{max}	Maximum observed concentration
CPA	Clinical Pharmacology Alliance
CK	Creatine kinase
CSP	Clinical Study Protocol
CSR	Clinical Study Report
CV	Coefficient of variation
CYP2C19	Cytochrome P450 2C19
DAE	Discontinuation of Investigational Product due to Adverse Event
DMP	Data Management Plan
DNA	Deoxyribonucleic acid
EDC	Electronic data capture
FSH	Follicle stimulating hormone
GCP	Good Clinical Practice
GMP	Good Manufacturing Practice
h	Hours
Hb	Hemoglobin

Abbreviation or	Explanation
special term	Explanation
HBsAg	Hepatitis B surface antigen
hCG	Human chorionic gonadotrophin
HIV	Human Immunodeficiency Virus
ICF	Informed Consent Form
ICH	International Conference on Harmonisation
IP	Investigational Product
IRB	Institutional Review Board
IUD	Intrauterine device
LIMS	Laboratory Information Management System
LLOQ	Lower Limit of Quantification
LSLV	Last Subject Last Visit
max	Maximum
NC	Not calculable
MedDRA	Medical Dictionary for Regulatory Activities
MI	Myocardial Infarction
min	Minimum
mIPA	Maximum inhibition of platelet aggregation
mPA	Maximum platelet aggregation
NSAID	Nonsteroidal anti-inflammatory drug
OAE	Other Significant Adverse Event
OTC	Over-the-counter
PCI	Percutaneous coronary intervention
PD	Pharmacodynamic
PR(PQ)	ECG interval measured from the onset of the P wave to the onset of the QRS complex.
PICTS	Phase I clinical trial system (brand name for Quintiles, Inc EDC)
pECG	Paper ECG
PK	Pharmacokinetic
PPI	Proton pump inhibitor
PRI	Platelet Reactivity Index
ΔPRI	Change from baseline in PRI

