- k. Day 1 samples will be obtained predose and 0.25, 0.5, 1, 1.5, 2, 4, and 6 hours postdose. Days 5, 14 and 29 samples will be obtained predose and 0.25, 0.5, 1, 1.5, 2, and 4 hours postdose
- 1. PD measurements (platelet aggregometry using 20 μM ADP and VASP) will be done prior to dosing to obtain measurements at baseline (Day -1 for Period 1 and Day1 for Periods 2 and 3) and then predose on Days 2, 6, and 15 as well as Day 30 (24 hours after the Day 29 dose).
- m. Baseline PD samples obtained on Day -1 for Period 1 only
- n. Baseline samples obtained on Day 1 for Periods 2 and 3, no Day -1 sample is collected for Periods 2 and 3.
- o. Standardized meals will be consumed on in-patient study days.
- p. All AEs will be collected from the time of the first administration of IP until the end of the study (including the follow-up visit). Before the first administration of IP, only SAEs will be collected.
- q. Volunteers will be discharged after all PK and PD assessments have been obtained

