7.1 Volume of blood [page 39]

Previous text:

Table 3	Volume of blood to be drawn from each volunteer			
Assessment		Sample volume ^a (mL)	No. of samples	Total volume (mL)
Safety	Clinical chemistry	8	11	88
	Alcohol screen	5	3	15
	PT/aPTT	3	3	9
	Hematology	4	11	44
	Viral serology	8	1	8
	S-hCG (females only) ^b	-	-	-
Pharmacodynamic	Platelet aggregometry	6	15	90
	VASP	5	15	75
Pharmacokinetic	Clopidogrel active metabolite	3	87	261
Genotyping	CYP2C19	2	1	2
Total Volume				592

a. If a cannula is used, 1 mL of blood will be taken to flush the cannula.

b. hCG for females will be measured using the sample obtained for clinical chemistry.

Revised text:

Table 3	able 3 Volume of blood to be drawn from each volunteer				
Assessment		Sample volume ^a (mL)	No. of samples	Total volume (mL)	
Safety	Clinical chemistry	8	11	88	
	Alcohol screen	5	3	15	
	PT/aPTT	3	3	9	
	Hematology	4	11	44	
	Viral serology	8	1	8	
	S-hCG (females only) ^b	-	-	-	
Pharmacodynamic	Platelet aggregometry	7	15	105	
	VASP	2.7	15	40.5	
Pharmacokinetic	Clopidogrel active metabolite	4	87	348	
Genotyping	CYP2C19	2	1	2	
Total Volume	, 		•	659.5	

a. If a cannula is used, 1 mL of blood will be taken to flush the cannula.

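### The ΔPRI formula in Protocol 11.3 divides by a Day 1 predose PRI that Period 1 does not schedule, and it leaves the difference unbracketed

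*Protocol*

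**What the plan says.** Protocol 11.3 gives the derivation: "Change in PRI calculated as [PRI (on Days 2/6/15/30) – PRI (at baseline) / PRI (on Day 1, predose)] × 100". The mIPA formula in the same section divides by baseline mPA and names no day.

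The sampling days are in the footnotes to Table 1 (Protocol 3.1). Footnote l gives the PD baseline as "Day -1 for Period 1 and Day1 for Periods 2 and 3". Footnote m adds "Baseline PD samples obtained on Day -1 for Period 1 only", and footnote n adds "Baseline samples obtained on Day 1 for Periods 2 and 3, no Day -1 sample is collected for Periods 2 and 3".

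Table 3 (Protocol 7.1) counts 15 VASP samples per volunteer. Amendment 1 changed the volume per sample but kept that count.

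The abbreviation list describes ΔPRI as "Change from baseline in PRI", with no division and no percent. The synopsis gives its status: "change in platelet reactivity index (Δ PRI), exploratory PD endpoints, will be assessed at these same time points". Protocol 12.2.5 nevertheless plans a mixed-model comparison of ΔPRI for each PPI arm against clopidogrel alone, with 90% confidence intervals and p-values.

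**The concern.** The formula subtracts one quantity (baseline) and divides by another (Day 1 predose), as though the two could differ. In Period 1 the second is not on the sampling schedule. In Periods 2 and 3 the two are the same sample, so without an inner bracket the quotient equals 1 and the baseline drops out of the result.

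A program written to this line would return missing ΔPRI for all of Period 1. Section 11.3 calculates PD variables only where the data permit, so those gaps could pass without being noticed. In the other two periods the program would return a rescaled post-dose PRI instead of a change. At stake is the planned treatment comparison for the first exploratory objective.

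**Working it through.** **Is there a Day 1 predose PRI in Period 1?** The PD schedule has one baseline and four later assessments (Days 2, 6, 15, 30) in each of three periods.

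- One baseline per period: 3 × (1 + 4) = 15, which reproduces Table 3.
- A Day 1 predose sample in Period 1 in addition to Day -1: 15 + 1 = 16, which does not.
- Amended Table 3: 15 × 2.7 mL = 40.5 mL, the stated total; 16 samples would need 43.2 mL.

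The sample count and the footnotes agree. The stated denominator is not scheduled in Period 1.

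**Share of data in Period 1.** In Figure 2, clopidogrel alone comes first in 6 of 18 sequences, and each PPI comes first in 4 of the 12 sequences that contain it. Both are one third. With 81 completers that is 81 of 3 × 81 = 243 volunteer-periods. If all 101 were dosed in Period 1 and every dropout came afterwards, the share would be 101/(101 + 81 + 81) = 38%.

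**The literal formula in Periods 2 and 3.** Baseline equals Day 1 predose, so

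[PRI_t − PRI_b/PRI_b] × 100 = (PRI_t − 1) × 100.

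The PRI values below are assumed, for illustration only:

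| Baseline → post-dose | Literal result | Percent change from baseline |
|---|---|---|
| 80 → 40 | 3900 | −50 |
| 70 → 70 | 6900 | 0 |
| 0.8 → 0.4 (PRI as a fraction) | −60 | −50 |
| 0.7 → 0.7 (PRI as a fraction) | −30 | 0 |

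**The formula with the difference bracketed.** [(PRI_t − PRI_b)/PRI_Day 1 predose] × 100 is correct in Periods 2 and 3, because there Day 1 predose is the baseline. Only Period 1 still fails.

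**Cost if Period 1 were lost: direct pairs.** Take any one PPI and its 12 sequences. Four start with clopidogrel alone, four start with that PPI, and four start with the other PPI. Only the last four keep both members of the pair in Periods 2 and 3. Protocol 12.3 plans 54 volunteers per PPI comparison, so 54 × 4/12 = 18 direct pairs remain.

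**Cost if Period 1 were lost: planned model.** Protocol 12.2.5 fits all treatments together, so volunteers without a direct pair still contribute through PPI-versus-PPI and other contrasts. I set out the 18 sequences with 81/18 = 4.5 volunteers each, fixed treatment, period and sequence, a random volunteer effect, and no site term. With σ_w² the within-volunteer variance, the variance of a PPI-minus-clopidogrel contrast is:

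- all three periods: 2σ_w²/60
- Periods 2 and 3 only: 2σ_w²/30

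The ratio of standard errors is √(60/30) = 1.41, the same at every intra-volunteer correlation tried from 0 to 0.9. Without the fixed sequence effect the ratio runs from 1.22 (correlation 0) to 1.40 (correlation 0.9).

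**The case against.** The strongest reply is that no data are missing. Table 1 schedules a predose baseline PRI in every period, and the formula itself already subtracts that baseline. An analyst who uses it as the denominator too can compute ΔPRI throughout. That is right, and it makes the Period 1 fault a wrong day label on a sample that exists. A reader might infer that a third of the ΔPRI data is irrecoverable; the sampling schedule does not support that.

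The second reply is that the bracketing is self-evidently a slip. The name of the variable, the abbreviation list and the objective all describe a change relative to baseline, and a formula returning 3900 for a halving cannot be what was meant. A stacked fraction may also have been flattened when the PDF was read. This stands as well. A reader might conclude that Periods 2 and 3 are wrong too, but that follows only from a literal operator order which the protocol's own description contradicts.

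Third, a reader who counts pairs might expect confidence intervals to widen by √(54/18) = 1.73. That ignores the indirect information in the mixed model of 12.2.5, where the factor is about 1.4, and even that applies only if Period 1 is actually dropped.

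Finally, a SAP could settle the derivation. That would be an answer if the protocol were silent, but it states a formula. Repairing the brackets alone still leaves Period 1 without its stated denominator, and neither protocol amendment shown changes 11.3.

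**Conclusion.** Wrong as written; severity minor to moderate. The certain part is that the stated denominator is not a scheduled sample in Period 1, which holds one third of planned volunteer-periods. Footnotes l, m and n and the Table 3 count establish this independently of each other. The missing inner bracket is a second fault in the printed expression, but under the evident intent it does no harm in Periods 2 and 3.

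The loss from 54 to 18 direct pairs and the standard-error factor of about 1.4 are conditional on the formula being programmed so that Period 1 drops out. They also assume 81 completers spread evenly over the 18 sequences, fixed sequence effects and no site term.

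The effect is confined to the exploratory ΔPRI endpoint. The primary endpoint, mIPA, is defined on baseline without a fixed day, and the sample size in 12.3 rests on mIPA alone, so neither is touched.

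**What to change.** Replace the line in 11.3 with

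ΔPRI = [(PRI on Day 2/6/15/30 − PRI at baseline) / PRI at baseline] × 100,

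and define baseline as the Day -1 value in Period 1 and the Day 1 predose value in Periods 2 and 3, the same period baseline as for mIPA. Amend the ΔPRI entry in the abbreviation list to say percent change from baseline, so that the scale is fixed in one way throughout.

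The cost is one corrected formula and one abbreviation entry, carried into the SAP and the programming specification. No additional samples are needed, and neither the schedule nor the sample size changes.

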12. STATISTICAL METHODS AND SAMPLE SIZE DETERMINATION

12.1 Description of analysis sets

12.1.1 Safety analysis set

All volunteers who received at least 1 dose of randomized IP and for whom any postdose data are available will be included in the safety population. Throughout the safety results sections, erroneously treated volunteers will be accounted for in the actual treatment group.

12.1.2 Pharmacokinetic analysis set

The PK analysis set will include all volunteers who receive clopidogel and have at least 1 quantifiable clopidogrel active metabolite concentration at a scheduled PK time point after start of dosing (with no important protocol violations thought to significantly affect the PK of the drug).

12.1.3 Pharmacodynamic analysis set

The PD population will consist of all volunteers who receive clopidogrel and have at least 1 platelet aggregation assessment at a scheduled PD time point after start of dosing (with no important protocol violations thought to significantly affect the PD of the drug).

12.2 Methods of statistical analyses

12.2.1 General Principles

The statistical analysis of the PK and PD variables, the individual PK figures and data listings will be the responsibility of the study biostatistician at Quintiles Overland Park, Kansas, USA (using SAS® version 9.1 or higher and, where appropriate, additional validated software). Quintiles SOPs and Work Instructions will be used as the default methodology if not otherwise specified.

Quantitative continuous variables will be summarized using descriptive statistics, including n, mean, standard deviation (SD), median, minimum, and maximum values. Additionally, for PK parameters, (except for t_{max}), geometric means and geometric coefficient of variation (CV) will be reported. The geometric mean is calculated as the exponential of the arithmetic mean calculated from data on a log scale. The CV% is calculated as $100 \cdot \sqrt{(exp(s^2)-1)}$ where s is the standard deviation of the data on a log scale. Mean, SD, geometric mean and CV% will not be calculated for t_{max} .

Data will be presented by treatment for the purposes of summarizing the study results. Missing data will result in a reduced sample size for that parameter. Since the statistical analyses will be predominantly presentations in tables and individual data listings, no action will be taken to handle missing data.

A healthy volunteer who withdraws prior to the last planned observation in a study period will be included in the analyses up to the time of discontinuation.

12.2.2 Volunteer characteristics

Continuous variables will be summarized using descriptive statistics (n, mean, SD, min, median, max) by treatment group. Categorical variables will be summarized in frequency tables (frequency and proportion) by treatment group.

12.2.3 Safety and tolerability

Continuous variables will be summarized using descriptive statistics (n, mean, SD, min, median, max) by treatment group. Categorical variables will be summarized in frequency tables (frequency and proportion) by treatment group.

All AEs will be collected for each volunteer from the time of admission until the follow up visit. Adverse events that occur before dosing will be reported separately.

Adverse events will be summarized by PT (Preferred term) and SOC (System organ class) using MedDRA vocabulary. Furthermore, listings of SAEs and AEs that led to withdrawal will be made and the number of volunteers who had any AEs, SAEs, AEs that led to withdrawal, and AEs with severe intensity will be summarized.

Tabulations and listings of data for vital signs (blood pressure and pulse), clinical laboratory tests, pECG assessments and interval data, and physical examination findings parameters will be presented. Where applicable, data will be summarized for the absolute value at each scheduled assessment, together with the corresponding changes from the baseline. For clinical laboratory tests, listings of values for each volunteer will be presented with abnormal or out-of-range values flagged. Clinical laboratory data will be reported in Système International (SI) units in the Clinical Study Report. Any additional conversion factors, if needed, will be applied on a case-by-case basis (Iverson et al 1998).

The pECG parameters will be summarized for the absolute value at each scheduled assessment, together with the corresponding changes from the predose value. The QT correction factor will be based on the Fridericia's formula. Further categorical summaries of absolute QT and QTcF values (greater than 450 ms, greater than 480 ms, greater than 500 ms) and change from predose values in QT and QTcF values (greater than 30 ms, greater than 60 ms) may also be presented.

12.2.4 Pharmacokinetics

Pharmacokinetic concentrations for clopidogrel active metabolite will be listed and summarized using descriptive statistics. For descriptive statistics, concentrations below lower limit of quantification (LLOQ) values will be handled as follows:

- At a time point where at least 1 value is above LLOQ but less than or equal to 50% of the values are below LLOQ, all values below LLOQ are set to LLOQ and a mean (arithmetic and geometric) value and SD and CV are calculated.
- At a time point where more than half of the observations are below LLOQ only individual values are reported; mean, SD, geometric mean and CV% will be set to NQ. The minimum (min) value and the median are set to less than LLOQ.
- If all values are below LLOQ at any time point, no descriptive statistics are calculated for that time point. Write NA (not applicable) in the field for standard deviation and less than LLOQ in fields for mean, min, median and maximum (max) in the table
- The number of observations greater than LLOQ [number of observations above LLOQ (N>LLOQ)] will be reported in the table.

Mean and individual concentration profiles and PK parameters will also be illustrated graphically. Graphical presentations of PK data may be added at the discretion of the PK scientist.

Data from volunteers excluded from an analysis population will be included in the data listings, but not in the summaries.

Pharmacokinetic comparison of test treatments (esomeprazole + clopidogrel, omeprazole + clopidogrel, or lansoprazole + clopidogrel) to the reference treatment (clopidogrel alone) will be assessed using the standard two one-sided t-tests approach. The PK parameters AUC, AUC_{0-t} and C_{max} for the clopidogrel active metabolite for each of the test treatments will be compared with the PK parameters for the reference treatment. Comparisons between the test and reference treatments will be made for each assessment day by using a mixed effects analysis of variance (ANOVA) model for each PK parameter (AUC, AUC_{0-t} and C_{max}). PK parameters will be analyzed on the natural log scale with fixed-effects for treatment, period, site, and sequence. Volunteers within sequence will be included as a random effect in the model. The linear contrasts subtracting the least-squares means for the reference treatment from the least-squares means for the test treatment will be estimated and exponentiated to obtain least square estimates of the ratios of geometric means and the corresponding 90% CI.

12.2.5 Pharmacodynamics

Descriptive statistics will be used to summarize mPA, and mIPA, in volunteers by treatment and by day. In addition, VASP data (PRI and Δ PRI) will be summarized using descriptive statistics by treatment and by day. All PD variables will be presented in listings.

Pharmacodynamic comparison of test treatments (esomeprazole + clopidogrel, omeprazole + clopidogrel, or lansoprazole + clopidogrel) to the reference treatment (clopidogrel alone) will be assessed for each of the PD endpoints – mIPA and Δ PRI. These PD endpoints for each of the test treatments will be compared with the corresponding PD endpoints for the reference

treatment. Comparisons between the test and reference treatments will be made by using a mixed effects analysis of variance (ANOVA) model with fixed-effects for treatment, period, site, and sequence. Volunteers within sequence will be included as a random effect in the model. Log-transformations may be used to meet model assumptions. The linear contrasts subtracting the least-squares means for the reference treatment from the least-squares means for the test treatment will be estimated to obtain least square estimates of the difference in least square means and the corresponding 90% CI. P-values will also be presented.

The above analysis will be repeated on mIPA excluding volunteers defined as clopidogrel low responders (mIPA response of 25% or less at Day 2) when receiving clopidogrel alone.

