7. BIOLOGICAL SAMPLING PROCEDURES

7.1 Volume of blood

The total volume of blood that will be drawn from each volunteer over approximately a 4.5 month period of time in this study is as follows:

Table 3	Volume of blood to be drawn from each volunteer			
Assessment		Sample volume ^a (mL)	No. of samples	Total volume (mL)
Safety	Clinical chemistry	8	11	88
	Alcohol screen	5	3	15
	PT/aPTT	3	3	9
	Hematology	4	11	44
	Viral serology	8	1	8
	S-hCG (females only) ^b	-	-	-
Pharmacodynamic	Platelet aggregometry	6	15	90
	VASP	5	15	75
Pharmacokinetic	Clopidogrel active metabolite	3	87	261
Genotyping	CYP2C19	2	1	2
Total Volume				592

a If a cannula is used, 1 mL of blood will be taken to flush the cannula.

The number of samples taken, as well as the volume required for each analysis, may be changed during the study.

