12.3 Determination of sample size

The study is sized to estimate the absolute mean difference in mIPA with and without the PPI with a specified precision. With 54 volunteers, a 95% CI with length of at most 9 percentage units is achieved with at least 96% probability. As each of the 3 PPIs is included in two-thirds of the planned treatment sequences, a total of 81 volunteers are required. Assuming a 20% dropout rate for this study, 101 volunteers will be enrolled to ensure 81 volunteers complete the study.

The calculation assumes an SD of paired difference of 14% units, derived from the root MSE of the analysis of internal data on ADP-induced maximum extent IPA for %mIPA (20 μ M ADP).

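### The mIPA model in Section 12.2.5 leaves out the period baseline mPA that the trial already collects: a low-cost efficiency gain of uncertain size, not an error

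*Protocol*

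**What the plan says.** Section 12.2.5 writes the pharmacodynamic model out in full. Comparisons with clopidogrel alone are "made by using a mixed effects analysis of variance (ANOVA) model with fixed-effects for treatment, period, site, and sequence", and "Volunteers within sequence will be included as a random effect in the model". The only latitude it leaves is a possible log-transformation.

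Section 11.3 defines the endpoint. mIPA is "Maximum inhibition of platelet aggregation calculated as" 100 × (1 − postdose mPA / baseline mPA), for Days 2, 6, 15 and 30.

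The footnotes to Table 1 in Section 3.1 fix when the baseline is drawn: "Baseline PD samples obtained on Day -1 for Period 1 only", and "Baseline samples obtained on Day 1 for Periods 2 and 3, no Day -1 sample is collected for Periods 2 and 3". In Table 3 of Section 7.1 the row "Platelet aggregometry" has 15 samples, and Amendment 1 changes their volume but not their number. Since 3 periods × (1 baseline + 4 postdose days) = 15, there is one baseline sample per period and no replicate.

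Section 12.3 sizes the trial on the precision of the mIPA difference. "The calculation assumes an SD of paired difference of 14% units", taken from the root MSE of an internal analysis of mIPA.

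**The concern.** Dividing by a baseline is not the same as adjusting for it. If the single draw reads high by chance, mIPA reads high on all four days of that period. The error is common to those days, so looking across days does not average it out. The random volunteer effect removes only what is constant over a volunteer's three periods, and this error is drawn afresh each period. It therefore stays in the within-volunteer residual, which is what determines the width of each PPI-versus-clopidogrel interval.

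Interval width is the trial's own design criterion. A covariate built from data already collected could shorten those intervals with no further volunteers or samples. At stake is efficiency only; the validity of the comparison is not in question.

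**Working it through.** **1. The plan's own figure.** Inputs from Section 12.3: n = 54 per comparison, SD of the paired difference 14, length at most 9 at 95% confidence. Length = 2 × t(0.975, 53) × S / √54.
- Length at S = 14: 7.64 points. Section 12.2.5 reports 90% intervals, for which it is 6.38.
- P(95% length ≤ 9) = P[χ²(53) ≤ 53 × (9√54 / (2t × 14))²] = 0.967. At n = 53 it is 0.957, so 54 is the smallest n that reaches 96%.
- 54 / (2/3) = 81, and 81 / 0.8 = 101.25, stated as about 101.

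The stated precision holds with no baseline covariate.

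**2. How baseline error enters.** To first order, one unit of baseline error moves mIPA by 100 × (1 − mIPA/100) / baseline. The protocol gives neither mean. With an assumed baseline mean of 75:
- mean mIPA 40%: 100 × 0.6 / 75 = 0.80 points per unit;
- mean mIPA 60%: 100 × 0.4 / 75 = 0.53 points per unit.

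A paired-difference SD of 14 implies a within-period variance of 14² / 2 = 98. The share due to baseline error is (slope × assay SD)² / 98:

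| Assay SD of mPA (assumed) | mIPA 40% | mIPA 60% |
|---|---|---|
| 2 | 1.6² / 98 = 2.6% | 1.07² / 98 = 1.2% |
| 4 | 3.2² / 98 = 10% | 2.13² / 98 = 5% |
| 5 | 4.0² / 98 = 16% | 2.67² / 98 = 7% |
| 6 | 4.8² / 98 = 24% | 3.2² / 98 = 10% |

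This approximates what a covariate could remove when the true baseline does not move between periods.

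**3. Simulation of the design.** The setting is 18 sequences, 81 volunteers, mean baseline 75, mean mIPA 40% on clopidogrel alone, a PPI effect of about −10, and noise tuned to a paired SD of about 14. The fit is within volunteer, with treatment and period, with and without the centred baseline. Reductions in the variance of the PPI contrasts from two separate simulations (3,000 and 2,000 runs per setting):

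| True between-period shift SD | Assay SD 4 | Assay SD 5 | Assay SD 6 |
|---|---|---|---|
| 0 | 12%, 13% | 19%, 20% | 30%, 27% |
| 4 | 6%, 4% | 11%, 12% | 21%, 17% |
| 8 | 2.5%, 1% | 6%, 4% | 10%, 11% |

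- With assay SD 2 or less, the change runs from a 2.4% fall to a 0.8% rise.
- The contrasts themselves did not move (for example −10.00 against −10.02).
- The no-shift entries somewhat exceed step 2 at 40%. The likely reason is that mIPA is about 30% in the PPI arms, where the slope is 100 × 0.7 / 75 = 0.93.
- A further simulation gave adjusted-to-unadjusted variance ratios of 0.74 to 1.01 at mean mIPA 40% and 0.90 to 1.006 at 60%.
- A small mixed-model check (25 runs per setting, one uncentred baseline term, sequence included) cut the SE by 3 to 5% at assay SD 4 and by 9 to 13% at assay SD 6, with shift SD 4 and 0. It showed no cut at SD 2.

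**4. In interval length.** A variance ratio of 0.70 gives 7.64 × √0.70 = 6.39 points. A ratio of 0.90 gives 7.64 × √0.90 = 7.25. A ratio of 1.01 gives 7.64 × √1.01 = 7.68.

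The runs in the table and the mixed-model check left out site, and neither fitted the two-covariate mixed model exactly as proposed below.

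**The case against.** The strongest reply is that the protocol states nothing wrong here. The contrasts are unbiased, no two sections conflict, and the precision target is met as written. The SD of 14 comes from an analysis of mIPA. If that mIPA was formed in the same way, baseline error is already inside the 14. All of this stands.

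The error enters through the ratio in Section 11.3 and not through the model. The ratio also does useful work, because it cancels true proportional shifts in baseline between periods. For that reason a covariate recovers only part of the error, and less as true shifts grow. This stands too, and it explains the falling gains down the columns of the simulation table.

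The size rests on four quantities that the protocol does not give: mean baseline, mean mIPA, assay SD and shift SD. Section 1.3 expects the clopidogrel effect to grow with repeated dosing, so a mean of 40% for every day is a favourable choice; at 60% the gain is much smaller. This stands, and it is why only a range is given.

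Finally, the centred covariate brings Period 2 and 3 baselines into the adjustment of Period 1. A predose draw in a randomised period is therefore not enough for unbiasedness: earlier treatment must also leave no trace in later baselines. Section 3.2 already assumes this, since it expects the 14-day washout to give complete platelet turnover, but the condition should be stated.

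What the reply does not remove is the asymmetry. The possible gain is material and the worst simulated loss is about 1% of variance.

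**Conclusion.** The point holds as an optional improvement in efficiency. The model omits a baseline that is collected once per period, whose error is shared by all four mIPA values of that period and is not absorbed by the volunteer effect.

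Under assumed values (mean baseline 75, mean mIPA 40 to 60%, assay SD 1 to 6, true shift SD 0 to 8, paired SD 14), adjustment changes the variance of the PPI contrasts by between about a 25 to 30% reduction and a 1% increase. The large gains need an assay SD near 6, mIPA near 40% and no true shift. The gain is near zero when assay SD is 2 or less, and it shrinks when mIPA is higher or baseline truly moves between periods.

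A reader might infer that the omission makes the primary intervals wider than planned, or biases them. The protocol supports neither. The intervals are wider only relative to a hypothetical adjusted model, the planned precision reproduces at 96.7% without adjustment, and the simulated contrasts were unchanged.

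**What to change.** In Section 12.2.5, keep mIPA as the endpoint and pre-specify two covariates in the mixed model:
- the period baseline mPA minus the volunteer's mean baseline mPA;
- the volunteer's mean baseline mPA.

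Using both keeps the within-volunteer and between-volunteer relations apart. Report the model without them as a sensitivity analysis. Add a sentence that the adjustment relies on no carry-over into later-period baselines, and refer to the washout rationale in Section 3.2. The choice must be written down before the data are seen. If the SAP already contains such terms, the protocol only needs to be brought into line. The same change for ΔPRI, with baseline PRI, is optional because that endpoint is exploratory; its gain was not calculated.

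The cost is two or three sentences and two model terms, with no new samples. The centred term takes one within-volunteer degree of freedom out of about 157 for a single day's analysis (243 observations − 81 volunteers − 2 for period − 3 for treatment). The mean term takes one between volunteers. For volunteers who drop out, the mean baseline comes from fewer periods, and the text should say how it is then formed.
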